*High mental illness burden among perinatal women with IPV:* There is mounting evidence from epidemiological studies that IPV markedly increases the risk of several psychiatric disorders. In general, IPV is associated with mental health burdens among women, that includes depression, posttraumatic stress disorder (PTSD), low-self-esteem, suicidal thinking, and suicide attempts. Specific to postpartum women, research has found a strong association between IPV and postpartum depression. Although no studies, to date, have focused exclusively on rates of psychiatric disorders found among pregnant women with IPV, research on perinatal women has found IPV-positive women to have a significantly higher rate of a current mood or anxiety diagnosis. In general, research has found prevalence rates of lifetime physical IPV among women with mental health disorders that range from 50% and above up to an astounding 75%. Furthermore, women who report bidirectional IPV report more mental health problems than IPV victims alone.

*Screening and intervention of perinatal women at mental health clinics is important because:* 1) A robust relationship exists between IPV and psychiatric disorders; 2) The presence of IPV reduces the utilization of mental health care; 3) In our study in which we conducted a retrospective chart review of 299 perinatal women attending mental health treatment, perinatal women with current victimization were more than twice as likely to leave treatment than those without current violence in their lives; 4) IPV and untreated mental illness pose a dual threat of adverse health outcomes to a perinatal woman and her developing fetus/infant; 5) Untreated psychiatric disorders are associated with partner revictimization and can interfere with IPV victims' ability to effectively use important shelter and community resources necessary for establishing safety for themselves and their children; 6) At least 20% of perinatal women seeking mental health treatment report ongoing interpersonal violence at

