**Site Differences:** In the preliminary analyses, participants from the two sites will be compared on all demographic and background information. We will also check for site effects with each specific hypothesis by including site as a fixed effect factor in the analysis. Site main effects and, as appropriate, interactions of site with relevant factors will be included. If site differences (and the interactions) are non-significant, this factor will be removed. Including site as a fixed effect and assuming an equal distribution of participants between sites and by treatment within each site will not change the overall sample size needed. However, the study may lack power to detect a site-by-treatment interaction unless the difference is large. Powering the study to detect the expected treatment effect separately by site is not feasible and would elevate the site-effect to a higher aim as opposed to being a check on the analysis[77].

**Aim 1:** For hypothesis 1 (primary outcome), the outcome (frequency of IPV) will be analyzed under a clustered count regression framework (Poisson or Negative Binomial) with frequency as outcome, and time (6-weeks, 3-, 6- and 12 months,), group (ROSE, control) and time-by-group interaction, with the

baseline (BL) IPV frequency as the primary covariate. A generalized linear mixed models (GLIMMIX) approach will be adopted by means of a random subject intercept to account for the clustering within each participant. Changes over time within each group will be estimated post-hoc by sliced effects derived from the regression model with adjustment for multiple comparisons. In additional analysis, reduction in proportion of participants experiencing a binary outcome of  $IPV \geq 1$  days within the 90-day period will be analyzed using a clustered logistic regression with a dichotomous outcome, again with BL IPV frequency as a covariate.

**Aim 2:** Similar analyses will be conducted for the secondary outcomes of positive affect and well-being and for perceived emotional support (Aim 2a and 2b). For cost estimation (Aim 2c) see below.

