**Aim 3:** The mediation tests will examine the ability of the proposed mediators, empowerment and self-efficacy, to account for all or part of the possible main effect of treatment on outcome. The mediators will be assessed at the end of treatment, and outcome will be taken from subsequent time points. We will use the product of coefficients test[78] to determine the magnitude and significance of mediated effects. This method multiplies the parameter estimate for the intervention predicting the mediator with the parameter estimate for the mediator predicting the outcome ( $\alpha\beta$ ). We will estimate the standard error and 95% confidence interval of  $\alpha\beta$  by bootstrapping, a re-sampling method that performs well when the assumption of normality may not hold.

**Missing Data:** Missing data will be handled by a weighted complete data analysis, using only complete cases after weighting the cases with the inverse probability of being missing. The probability is calculated as a function of the variables that are simultaneously associated with the outcome of interest and the event of being missing itself.

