**Power:** We calculated the sample size using mean, standard deviation, and within-subject correlation estimates for IPV frequency from our R21 study. IPV frequency was measured by the CAS Total score. In our pilot data, we observed participants in ROSE demonstrated a significantly larger change in frequency of IPV than the control condition. The observed between-group effect size for change in IPV frequency at follow up was moderate to large: Cohen's  $d$  of 0.59 and 0.68 with and without adjustment for baseline score. Therefore, a more conservative effect size of  $d = 0.4$  was selected for sample size estimation. With four follow up IPV assessments, a within-subject correlation of 0.62, and a standard deviation of 20, 74 participants per group are needed to detect an effect size of  $d = 0.4$  for the overall intervention vs. control group difference with 80% power at the 5% significance level. A minimum effect size of  $d = 0.4$  will be detectable for the secondary outcomes of positive affect and well-being and perceived emotional support. The secondary outcome measures are reported as T-scores based on a normative mean of 50 and standard deviation of 10. With 74 patients per group and assuming an observed SD of 10, a 4-point difference in positive affect and well-being or perceived emotional support will be detectable. Moderate effect sizes (Cohen's  $f$  for multiple regression = 0.39) for mediated effects of the intervention ( $\alpha$  and  $\beta$ ) will be detectable with 80% power and 74 patients per group[79]. For all the outcomes, our proposed sample of 186 should be adequate for detecting small to moderate effect sizes. Even assuming the worst-case scenario of up to 20% drop-out in both the ROSE and control groups, we plan to recruit 93 participants per arm.

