## 6. WITHDRAWAL OF SUBJECTS

Study staff will be trained on understanding the various potential risks of participation in this study, as explained above, in the section "Risks and Benefits." As explained in this section, various procedures will be put into place to mitigate these potential risks. However, if when discussing the safety of a subject's participation in the study, study staff decides that stopping a subject's participation is necessary for safety reasons, then study staff will withdraw the subject from the study. As explained in the "Risks and Benefits" section, we anticipate that potential circumstances in which this might need to occur include breaching of confidentiality, coercion of participants, participant discomfort, the occurrence of study-related partner violence, and/or social or legal consequences related to study participation.

If participants voluntarily withdraw from the research, study staff will keep the data that has already been collected, and will use this data in the study analysis procedures. If a participant is physically present when she decides to withdraw from the study, she will be checked in with by research staff, be given any relevant informational handouts if it is safe for her to receive and take with her, and be given any relevant referrals.

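### The missing-data weight is inverted: a complete case should be weighted by one over its probability of being observed, not of being missing

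*Combined protocol and SAP*

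**What the plan says.** The Missing Data paragraph in section 4 (Data Management) sets out a weighted complete-data analysis, "using only complete cases after weighting the cases with the inverse probability of being missing". It describes that probability as one "calculated as a function of the variables that are simultaneously associated with the outcome of interest and the event of being missing itself". No other part of the document gives a missing-data method or restates the weight.

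The Aim 1 paragraph fits a Poisson or negative binomial mixed model to the four follow-up visits, with baseline IPV frequency as covariate, "by means of a random subject intercept to account for the clustering within each participant". For Aims 2a and 2b, "Similar analyses will be conducted for the secondary outcomes of positive affect and well-being and for perceived emotional support". The Power paragraph allows for a "worst-case scenario of up to 20% drop-out in both the ROSE and control groups".

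**The concern.** Inverse-probability weighting lets the women who stayed stand in for similar women who left. That needs a weight of 1/P(observed), which rises with the chance of loss. The stated weight, 1/P(missing), falls as the chance of loss rises, so it moves the sample further from the one randomised. The sentence on how the probability is modelled does not repair this, because it too describes the event of being missing.

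The rule governs the primary outcome and, through the Aim 2 sentence, well-being and emotional support. Loss related to IPV is plausible on the plan's own evidence. The Background reports from a chart review that "perinatal women with current victimization were more than twice as likely to leave treatment than those without current violence in their lives". That is only a guide: it concerns leaving treatment rather than leaving a study, and every trial participant has past-year IPV.

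**Working it through.** **Inputs from the Power paragraph.** Up to 20% loss per arm, 74 evaluable and 93 recruited per arm, SD 20, within-subject correlation 0.62, d = 0.4 (0.4 × 20 = 8 CAS points).

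**Assumed.** Two equal halves, low and high CAS, with means 10 and 30 (true mean 20.0). Average loss is 20%, split 13.3%/26.7% (2:1) or 10%/30% (3:1). The document gives neither split.

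**Plan's own figure.** 74/(1 − 0.20) = 92.5, so 93 per arm. The weight does not enter this calculation.

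**Step 1, weights (low/high half).**
- 2:1, as written: 1/0.1333 = 7.5 and 1/0.2667 = 3.75. Correct: 1/0.8667 = 1.15 and 1/0.7333 = 1.36.
- 3:1, as written: 10 and 3.33. Correct: 1.11 and 1.43.

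**Step 2, weighted mean.** Each half contributes P(observed) × weight.
- 2:1, as written: 0.8667 × 7.5 = 6.5 and 0.7333 × 3.75 = 2.75. The high half counts 2.75/9.25 = 30% instead of 50%. Mean = (6.5 × 10 + 2.75 × 30)/9.25 = 15.9.
- 2:1, unweighted: (0.8667 × 10 + 0.7333 × 30)/1.6 = 19.2.
- 3:1, as written: contributions 9 and 2.333, high half 21%, mean (90 + 70)/11.333 = 14.1. Unweighted: (9 + 21)/1.6 = 18.75.
- Correct weight: each half contributes 1, so the mean is 20.0 in both cases.

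**Step 3, same loss in both arms, constant effect of −8.** ROSE means are 2 and 22. As written, 2:1: (6.5 × 2 + 2.75 × 22)/9.25 = 7.95, against 15.95 in control. The difference is −8.0, so there is no contrast bias.

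**Step 4, loss following CAS in one arm only (simulation).** Settings: 4,000 replicates; 93 per arm; SD 20; exchangeable correlation 0.62; assumed mean 20; baseline CAS as covariate; true effect −8; loss at 3, 6 and 12 months following 6-week CAS in one arm, and 20% in both halves of the other. The loss probability was estimated per arm-by-half cell, and the few replicates with a zero-loss cell (0% to 1.9%) were left out. Results at 2:1:

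| How the weight is applied | Loss follows CAS in control arm | Loss follows CAS in ROSE arm |
|---|---|---|
| Whole woman, three later visits, as written | −6.4 | −9.6 |
| Same, unweighted | −7.7 | −8.3 |
| Same, correct weight | −8.0 | −8.0 |
| Per visit in the four-visit random-intercept model, as written | −8.0 | −8.0 |

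A count-scale check (negative binomial random-intercept model, 400 replicates, true rate ratio 0.60) agrees. Per-visit weights as written give 0.60 to 0.61. Whole-woman weights on four-visit completers give 0.67 or 0.55 at 2:1.

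**Step 5, effect varying with severity.** Assume −4 in the low half and −12 in the high half (average −8), with the same 2:1 loss in both arms driven by baseline CAS. Whole woman, as written: (6.5 × −4 + 2.75 × −12)/9.25 = −6.4. Per visit in the random-intercept model: −7.5 as written, against −7.9 unweighted.

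**Step 6, precision (2:1 in both arms).** With whole-woman weights on the three later visits, the SD of the contrast is 2.45 as written and 1.99 with the correct weight, a variance ratio of (2.45/1.99)² = 1.5. Per visit it is 1.81 against 1.80.

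**The case against.** The strongest reply is that this is a slip of the pen. The paragraph describes a recognised method, and a competent statistician would build 1/P(observed) without comment. That may be so. But the document never states the right weight, so the analyst must either follow the text and use an invalid weight, or depart from the prespecified plan for the primary outcome.

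The second reply is that the harm to the treatment contrast is unproven. This largely stands. The shifts in step 4 need whole-woman weighting, loss tied to CAS in one arm only, and 20% loss. The Power paragraph treats 20% as a worst case and describes no arm-specific pattern, and the Objectives section reports 92% follow-up at 4 months in the pilot. Per-visit weighting under the Aim 1 model removes nearly all of the bias. However, the restriction to complete cases can also be read as whole-woman weighting, so the per-visit result limits the harm without ruling it out.

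A reader might infer three stronger things that the document does not support:
- **That the primary contrast is biased by a known amount.** The same assumed 3:1 loss in the control arm gives −5.7, −4.7 or −8.0, depending on whether whole women (three later visits), four-visit completers or single visits are weighted.
- **That the weight often could not be computed.** It is undefined only where estimated loss is exactly zero, and extreme where it is near zero. Frequent failure arises when loss is estimated separately in small arm-by-severity cells. The plan does not specify that, and a main-effects logistic model rarely or never fails.
- **That section 6 dictates per-visit weighting.** It says that after voluntary withdrawal "study staff will keep the data that has already been collected, and will use this data in the study analysis procedures", but it sets no unit for the weight.

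**Conclusion.** The weight is wrong as written and should be corrected. Where loss depends on severity, it is worse than no weighting: in the illustration the mean of 20.0 becomes 15.9 (2:1) or 14.1 (3:1), against 19.2 or 18.75 unweighted. Those sizes rest on the assumed halves, means and splits. The direction follows from the formula whenever the loss probability varies with the outcome. If no variable predicts loss, the weights are constant and do no harm.

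No single figure can be given for the treatment contrast. It ranges from no bias (same loss in both arms with a constant effect, or per-visit weighting in most cases tested) to a shift of about 1.6 points either way at 2:1, from −8 to −6.4 or −9.6, under whole-woman weighting with one-arm loss. Precision is also worse under whole-woman weighting.

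**What to change.** In the Missing Data paragraph, define the weight as the inverse of the probability of being observed, that is, 1 divided by (1 minus the modelled probability of being missing). The cost is one sentence of wording. No participants, visits or staff are added, and 74 evaluable and 93 recruited per arm are unchanged.

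Two separate, optional additions go beyond this correction. One is to state whether the weight applies per woman or per visit, since the consequences differ so much. The other is a sensitivity analysis for loss driven by the unobserved CAS value, which no estimable weight can correct.

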**Protection against risk**

We will take the following steps to protect against risks associated with this research project:

*We will minimize the risk of breach of confidentiality.*

Risk of social or legal consequences as a result of disclosure of IPV within the past year will be dealt with in several ways. We will minimize the potential risks due to loss of confidentiality by strictly adhering to the guidelines for research outlined by Women and Infants Hospital IRB, Rhode Island state law and the DHHS Federal Policy for the Protection of Human Subjects (45 CFR Part 46 Subpart D). As described in the previous section, there will be full informed phone or in-person consent prior to participation in the study (a two-part consent process). Participant data will be encrypted in transit between user and server. No identifying information will be entered into the ACASI. The use of a linking table will provide the participant with confidentiality as the link between the participant code number and name will be kept in a password protected file on password protected computer. Lastly, potential participants will be informed of the situations in which they may not be protected under the Certificate of Confidentiality. No information about participants will be released without their permission or where required by law.

Possible distress due to sensitive items will be noted clearly in the informed consent information sheet (for screening) and in the written informed consent form (for participants). All participants will be told that they can skip any question or quit at any time if they become uncomfortable. To further address possible distress due to sensitive items, participants will be periodically asked by the research assistant (RA) if anything the RA has asked or done is making them feel upset right now. For both the online intervention and in-person computer-delivered intervention, the research assistant will contact the participant after 40 minutes, the time it takes to watch the intervention and inquire if anything in the intervention distressed her. At a minimum, all participants indicating some distress will be given a list of referral options. If in treatment women will be encouraged to contact their mental health provider.

*We will minimize the risk of study-related partner violence.*

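### Read in its ordinary sense, the complete-case rule discards recorded follow-up abuse scores that the planned mixed model could use, and its weights are stated the wrong way round.

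*Combined protocol and SAP*

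**What the plan says.** All references are to the combined protocol and SAP.

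- **Section 4, Missing Data.** This is the only missing-data rule. The analysis is a weighted one, "using only complete cases after weighting the cases with the inverse probability of being missing". On the weights it adds: "The probability is calculated as a function of the variables that are simultaneously associated with the outcome of interest" and with missingness itself. It does not say whether a case is a woman or a visit.
- **Section 4, Aim 1.** The primary model is a Poisson or negative binomial mixed model over 6 weeks and 3, 6 and 12 months, with baseline frequency as the primary covariate. Repeated scores are handled "by means of a random subject intercept to account for the clustering within each participant".
- **Section 4, Power.** "With four follow up IPV assessments, a within-subject correlation of 0.62, and a standard deviation of 20, 74 participants per group are needed" for d = 0.4 with 80% power at 5%. Recruitment is set at 93 per arm to allow for a "worst-case scenario of up to 20% drop-out in both the ROSE and control groups".
- **Section 6, Withdrawal of Subjects.** For women who leave voluntarily, "study staff will keep the data that has already been collected, and will use this data in the study analysis procedures". Staff may also end participation: if stopping "is necessary for safety reasons, then study staff will withdraw the subject from the study". Nothing is said about using the data of women withdrawn in that way.

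**The concern.** A woman who gives CAS scores at 6 weeks, 3 months and 6 months and then misses month 12 is not a complete case in the ordinary sense. Under the rule, her three scores do not enter the primary comparison. A random-intercept model does not need all four scores, so the rule gives up information that the chosen model could use. It also fits poorly with the section 6 statement on voluntary leavers. What is at stake is the width of the confidence interval for the primary effect. There is also a risk that two analysts following the same paragraph would build different primary data sets.

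The wording of the weights is a separate fault. To let complete women stand in for incomplete ones, each is weighted by one over her probability of being complete. The text says the inverse of the probability of being missing.

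**Working it through.** **Inputs.** SD 20, within-subject correlation 0.62, four follow-ups, d = 0.4 (8 CAS points), 93 per arm and 20% drop-out come from section 4, Power. The 92% follow-up rate is the pilot's single 4-month figure (section 1, Objectives). The plan gives no visit-by-visit missingness, so the patterns below are assumptions.

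**The plan's own figure.** The mean of four correlated scores has variance factor (1 + 3 × 0.62)/4 = 0.715, so its SD is 20 × √0.715 = 16.91. A two-sided 5% test for 8 points with 80% power needs 71 per group (normal formula) or 72 (t formula). The plan's 74 gives about 82% power. Then 74/0.80 = 92.5, rounded up to 93, and 93 × 0.80 = 74.4. The plan's arithmetic stands, and it counts women with full follow-up.

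**Formula for the planned, baseline-adjusted comparison.** Assume baseline CAS also correlates 0.62 with each follow-up. After adjustment, the covariance between follow-ups is 400 × (0.62 − 0.62²) = 400 × 0.2356, and the remaining visit-level variance is 400 × 0.38. A woman with k scores contributes information

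I(k) = k / [400 × (0.38 + 0.2356k)]

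which gives I(1) = 0.00406, I(2) = 0.00587, I(3) = 0.00690 and I(4) = 0.00756. Then SE = √(2 / information per arm) and power = Φ(8/SE − 1.96).

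**20% drop-out: 74.4 complete and 18.6 incomplete women per arm.**

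- Complete women only: 74.4 × 0.00756 = 0.5626, so SE = 1.885.
- Drop-out spread evenly over 0, 1, 2 and 3 completed follow-ups (4.65 women each): add 4.65 × (0.00406 + 0.00587 + 0.00690) = 0.0783. SE = √(2/0.6409) = 1.767.
- All miss only month 12: add 18.6 × 0.00690 = 0.1284. SE = √(2/0.6910) = 1.701.
- All leave before 6 weeks: nothing to add.

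**Independent misses of 8% at each visit.** The complete share is 0.92⁴ = 0.716, or 66.6 women per arm, so SE is 1.992 for complete women and 1.712 for all scores. If instead the same women always miss, 93 × 0.92 = 85.6 per arm are complete and nothing is lost.

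| Pattern | Recorded scores discarded | SE, complete women | SE, all scores | Ratio | Power |
|---|---|---|---|---|---|
| 20%, all before 6 weeks | 0 | 1.885 | 1.885 | 1.00 | 0.99 both |
| 20%, spread evenly | 56 of 651 (9%) | 1.885 | 1.767 | 1.07 | 0.989 vs 0.995 |
| 20%, month 12 only | 112 of 707 (16%) | 1.885 | 1.701 | 1.11 | 0.989 vs 0.997 |
| 8% of visits, independent | 151 of 684 (22%) | 1.992 | 1.712 | 1.16 | 0.980 vs 0.997 |

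Scores discarded, both arms: 37.2 × 1.5 = 55.8 of 186 × 0.80 × 4 + 55.8 = 651; 37.2 × 3 = 111.6 of 706.8; 151.5 of 186 × 4 × 0.92 = 684.5.

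**How far this depends on the approximation.** Without baseline adjustment the ratios are 1.08, 1.11 and 1.17, so the relative loss barely depends on the assumed baseline correlation. The formulas are a linear stand-in for the count model and ignore any effect of weighting on variance. A simulation of 120 trials used a negative binomial random-intercept model with log baseline as covariate (assumed mean 20, rate ratio 0.6, 20% drop-out spread over 0 to 3 visits). It gave a mean SE of the log rate ratio of 0.0833 for complete women and 0.0782 for all scores, a ratio of 1.07.

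**The weights.** Compare two complete women whose probabilities of being incomplete were 8% and 20% (illustrative). Correct weights are 1/0.92 = 1.09 and 1/0.80 = 1.25. Literal weights are 1/0.08 = 12.5 and 1/0.20 = 5. The literal rule gives more weight to the woman who least needs it.

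**The case against.** The strongest reply is that a case may be a visit. The Aim 1 model is fitted to visit records clustered within women, and section 6 says leavers' data will be used, so a visit-level reading removes the conflict. That stands as a possible reading, and on it no recorded score is lost. But the text does not say so. The sample size counts women with full follow-up (74.4 of 93), and the ordinary sense of a complete case in a repeated-measures trial is a participant.

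Section 6 does not promise that every score enters the primary model. Leavers' data could also be used in the weight model or the baseline comparisons, and the statement covers voluntary withdrawal only. That is fair. For women who merely miss a visit, the argument rests on what the model can use, not on section 6.

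Weighted complete-case analysis is also a recognised method. That is why it is worth keeping, as a sensitivity analysis.

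**Conclusion.** A minor point, held with medium confidence because it depends on the woman-level reading. On that reading the rule costs precision in the primary comparison: 0% to 11% on the standard error at the plan's 20% drop-out, and about 16% if 8% of visits are missed independently. Adjusted power at d = 0.4 stays at or above 0.98. The weight wording needs correcting on either reading.

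Three stronger conclusions that a reader might draw are not supported.

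- **That the rule leaves the trial underpowered.** At 20% drop-out, 74.4 women per arm remain and the stated 80% is met. A figure below 80% (0.78) appears only without baseline adjustment, which is not the planned model, and with independent misses that leave 28% of women incomplete, beyond the plan's worst case.
- **That the rule biases the result through safety withdrawals.** The documents give neither withdrawal rates nor a list of weighting variables. Bias from violence that is never recorded would not be removed by fitting the mixed model either, so it is not a consequence of this rule.
- **That skipped questions make matters worse.** Women "can skip any question or quit at any time if they become uncomfortable", but if a skipped item voids a CAS total, that score is missing for the mixed model too.

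**What to change.** 1. In section 4, make the primary analysis the Aim 1 mixed model fitted to every recorded follow-up CAS score from every randomised woman, whether she completed, missed visits, left voluntarily or was withdrawn by staff.
2. Keep the weighted complete-case analysis as a sensitivity analysis. Define a case there as a woman with all four follow-up scores, and set the weights to one over the probability of being complete.
3. In section 6, extend the statement on keeping and using data to women withdrawn by staff.

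If the sponsor always meant a visit-level case, a sentence saying so, together with the weight correction and item 3, is enough.

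The cost is a few sentences, with no change to sample size, visits or safety decisions. The downside is that the mixed model still assumes that missingness depends only on observed data.

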### Aim 1 (Primary Outcome)

To test the hypothesis that ROSE, compared to an attention, time and information matched control condition, will be associated with a lower frequency of IPV among perinatal women seeking mental health treatment at 6-weeks, 3 months, 6 months, and 12 months follow up.

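### The rule for building the missing-data weights does not ensure that arm or arm-by-predictor terms enter, so bias from drop-out whose drivers differ by arm may remain

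*Combined protocol and SAP*

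**What the plan says.** The Missing Data paragraph of Section 4 (Data Management) sets the analysis as "using only complete cases after weighting the cases with the inverse probability of being missing", with that probability taken to be "a function of the variables that are simultaneously associated with the outcome of interest and the event of being missing itself". It lists no predictors and gives no threshold for association. It does not say whether weights are built by arm or by visit. Arm is neither required nor excluded. The documents contain no missing-data sensitivity analysis.

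The primary model, under Aim 1 of Section 4, has terms for time, "group (ROSE, control) and time-by-group interaction", with "baseline (BL) IPV frequency as the primary covariate". The Power paragraph allows for "up to 20% drop-out in both the ROSE and control groups", the same figure for each arm.

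**The concern.** Drop-out threatens a randomised comparison mainly when the women who leave one arm differ, on the outcome, from the women who leave the other. The weights are the plan's only stated remedy, so they need to let the drop-out mechanism differ by arm. The rule does not secure this, for three reasons.

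- If the arms lose equal shares for different reasons, arm has no overall association with missingness and fails the rule.
- If ROSE has no effect, arm has no true association with the outcome and fails again. That is the case in which type I error is defined.
- If arm does pass, it enters as one variable. The rule never asks for arm-by-predictor terms, and those are what this mechanism needs.

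Outcome-related loss is plausible here. The Background reports, from the team's own chart review, that "perinatal women with current victimization were more than twice as likely to leave treatment than those without current violence in their lives". That finding concerns leaving mental health care, not study follow-up, and it says nothing about arm. It supports concern about outcome-related loss, not its size or direction.

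**Working it through.** **The plan's own figures.** From the Power paragraph: SD 20, d = 0.4 (8 CAS points), four follow-ups, within-subject correlation 0.62, 80% power, 5% level (taken as two-sided). The variance factor for the mean of four visits is (1 + 3 × 0.62)/4 = 0.715, so the variance is 400 × 0.715 = 286. Then n = 2 × (1.960 + 0.842)² × 286/8² = 70.1, rounded up to 71 per group, or 72 by the t distribution. The plan's 74 gives about 82% power. Allowing for 20% loss, 74/0.8 = 92.5, rounded up to 93. Expected losses are 93 − 74 = 19 per arm.

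**Standard errors at 74 per arm.**
- Unadjusted: √(2 × 286/74) = 2.78.
- Baseline-adjusted, assuming 0.62 is also the correlation with baseline: √(2 × 400 × (0.715 − 0.62²)/74) = 1.89.

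Both ignore extra variability from the weights.

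**Assumed drop-out.** 40% of women are high-risk and score g points higher beyond what baseline CAS explains. ROSE retains 80% of both groups. Control retains 60% of high-risk and 93.3% of other women (strong pattern), or 70% and 86.7% (mild pattern). Each arm then retains 80% overall; for example, 0.4 × 0.60 + 0.6 × 0.933 = 0.80.

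**Strong pattern.** Without weights, the high-risk share of completers is 0.24/0.80 = 0.300 in control and 0.32/0.80 = 0.400 in ROSE, a difference of 0.100. The pooled probabilities of being observed are 0.70 and 0.867. Weighting by their inverse gives:
- control: (0.24/0.70)/(0.24/0.70 + 0.56/0.867) = 0.347
- ROSE: (0.32/0.70)/(0.32/0.70 + 0.48/0.867) = 0.452

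The difference is 0.1055, so pooled weights do not reduce the imbalance. Arm-specific weights return both shares to 0.40.

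**Mild pattern.** Pooled probabilities of 0.75 and 0.833 give shares of 0.374 and 0.426, a difference of 0.0512 (0.050 unweighted).

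**Bias and type I error.** Bias is g times the difference in share. With Φ the standard normal distribution function, type I error is Φ(−1.96 + bias/SE) + Φ(−1.96 − bias/SE). The lower figure in each range uses SE 2.78 and the higher uses 1.89.

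| Gap g | Pattern | Bias, pooled weights | Type I error | Bias, arm-specific weights |
|---|---|---|---|---|
| 10 | mild | 0.51 | 5.4–5.8% | 0 |
| 10 | strong | 1.06 | 6.7–8.6% | 0 |
| 20 | mild | 1.02 | 6.6–8.4% | 0 |
| 20 | strong | 2.11 | 11.8–20.0% | 0 |

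**How large g can be.** Stable between-woman variance left after baseline is 400 × (0.62 − 0.62²) = 94.2. A 40% group with gap g uses 0.4 × 0.6 × g². At g = 20 this is 96, slightly more than all of it. At g = 10 it is 24, about a quarter. Ten points is therefore the working value and 20 the upper bound.

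**Which mechanisms matter.** A large-sample simulation used 1,000,000 women per scenario, normal outcomes at one visit, and inverse-probability-of-being-observed weights. The slopes of drop-out on IPV were assumed at 0.7 log-odds per SD, and Monte Carlo error was about 0.05 points. Bias in the 12-month arm difference is shown unadjusted / baseline-adjusted; negative values favour ROSE.

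| Drop-out depends on | True effect | No arm in weights | Arm main effect | Arm-by-covariate terms |
|---|---|---|---|---|
| arm only (30% vs 10%) | 0 | 0.01 / −0.03 | 0.00 / −0.03 | 0.00 / −0.03 |
| baseline IPV, opposite by arm | 8 | −3.28 / 0.02 | −3.28 / 0.02 | 0.02 / 0.02 |
| 6-week IPV, opposite by arm | 8 | −2.92 / −1.07 | −2.90 / −1.06 | 0.05 / 0.08 |
| 6-week IPV, opposite by arm | 0 | −3.31 / −1.34 | −3.31 / −1.34 | −0.04 / −0.07 |

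An arm main effect changes nothing when the drivers differ by arm; arm-by-covariate terms remove the bias.

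**The case against.** The text gives no functional form. It bars neither arm nor interactions nor fitting by arm. Aim 1 expects that ROSE "will be associated with a lower frequency of IPV among perinatal women seeking mental health treatment"; if that is so and drop-out rates differ, arm meets both conditions and is selected. A reader might infer that the rule always leaves arm-specific drop-out out, or that the weights cannot remove the bias. The documents support neither. They support only that nothing guarantees arm or its interactions will enter.

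Requiring both associations is not itself the flaw, and unequal drop-out is not in itself biasing. Loss that depends on arm alone causes none, and loss driven by arm and baseline IPV causes none once the planned baseline covariate is in the model. What remains is drivers beyond baseline, such as IPV after randomisation or living circumstances. The planned random-intercept model could use the early visits of women who later drop out, but the restriction to complete cases gives that up.

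The mechanism is assumed. Against it, the Objectives report 92% follow-up at 4 months in the pilot, the Control Condition section reports equal acceptability in both arms in earlier studies, and both arms share one follow-up schedule. This lowers the likelihood but does not settle a 12-month trial planned with 20% loss.

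That arm-specific models cost precision is a fair worry with few losses. In a simulation at 93 per arm with three predictors and a 10-point gap, they cut the bias from about 1.1 to 0.05 points, and the SD of the estimate was 1.87–1.92 against 1.90–1.96 with pooled weights.

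**Conclusion.** The concern stands in a limited form: the weight rule does not ensure protection against drop-out whose drivers differ by arm beyond baseline CAS. Correcting the weights to the inverse probability of being observed, which is needed separately, does not cure this.

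Under the assumed 40% high-risk group, 10-point gap and 80% retention per arm, the bias is about 0.5 to 1.1 CAS points, or 6% to 14% of the 8-point design effect, with type I error of about 5.4% to 9%. The 20-point case should not be read as the expected size, because it uses up all the stable variation beyond baseline. The direction is open: the worked example runs against ROSE, and the reverse pattern would favour it. The simulation used normal outcomes rather than the planned count model, so its sizes are illustrative. The change is worth making because it is cheap and the plan has no other safeguard.

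**What to change.** Replace the sentence that defines the probability with: *The probability of being observed is modelled separately in each arm (or with arm and arm-by-predictor terms always included), using a small prespecified set of predictors already collected, such as current relationship to the abuser, site, baseline CAS and, for later visits, the earlier-visit CAS.* Amend the preceding sentence so that complete cases are weighted by the inverse of that probability.

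Predictors beyond baseline CAS deserve priority, since baseline CAS is already in the outcome model. If earlier-visit CAS is used, the plan should say that weights are built by visit and how a missed earlier visit is handled.

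The cost is a short edit to the analysis plan, with no new data and no change in sample size. The limit is that about 19 losses per arm support only two or three predictors in each arm-specific model.
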